### 13.0 Study Plan

#### 13.1 \* Describe the study plan:

Select a template:  Select an arm:

Procedure/Task Name	CPT Code	Screening ...	Screening ...
Clinical Procedures			
Adverse Event Assessment			
Adverse Event /Serious Adverse Event Assessment			1
Assessments (Nursing)			
Assess for changes in general health status			1
Blood Pressure Seated		1	
Concomitant Medications			

\* What is the total number of outpatient visits for all subjects projected for the next year?

240

\* What is the average length of each outpatient visit (in hours)?

2

\* What is the total number of Day Patients visits for all subjects projected for the next year?

0

\* What is the average length of each Day Patient visit (in hours)?

0

\* What is the total number of inpatient days for all subjects projected for the next year?

0

#### 13.2 \*Number of Patients per arm

Study Arm	Number of Patients
Healthy Controls	20

## 14.0 Study Drugs

### 14.1 \* List all the medications, study drugs, biological agents, solutions and supplements needed to conduct the study:

See Help for link to Rockefeller University Research Pharmacy web page for additional information.

**View Details**   **Drug Name**   **FDA Approved**   **IND Number**

**Trade Drug Name:** Fluarix Quadrivalent  
**Generic Drug Name:** Influenza Vaccine   **FDA Approved:** Yes  
**Investigational Drug Name:**

Trade Drug Name:	Fluarix Quadrivalent
Generic Drug Name:	Influenza Vaccine
Investigational Drug Name:	
Identify the name of the manufacturer or source of investigational drug/biologic:	GlaxoSmithKline
Is the Drug FDA Approved:	Yes
Is an IND necessary	No
IND Number	
Who holds the IND:	N/A
IND details:	
Are you currently using this IND in another research project?	No
If yes, list the IRB Number(s):	
Dose Range:	0.5mL prefilled syringe

**Trade Drug Name:** Fluzone Quadrivalent  
**Generic Drug Name:** Influenza Vaccine   **FDA Approved:** Yes  
**Investigational Drug Name:**

Trade Drug Name:	Fluzone Quadrivalent
Generic Drug Name:	Influenza Vaccine
Investigational Drug Name:	
Identify the name of the manufacturer or source of investigational drug/biologic:	Sanofi Pasteur
Is the Drug FDA Approved:	Yes
Is an IND necessary	No
IND Number	
Who holds the IND:	N/A
IND details:	
Are you currently using this IND in another research project?	No
If yes, list the IRB Number(s):	
Dose Range:	0.5mL prefilled syringe

### 14.2 \* Will the study involve the use of a placebo?

Yes    No

If yes, complete A and B.

A. Is there a proven effective therapy for the condition under study?

Yes    No

If Yes, please specify:

B. Please give a justification for the use of the placebo.

**15.0 Consent Procedure****15.1 \* This study will use the following types of informed consent:**

- Informed Consent Form Standard - a standard consent form with instructions for adapting it to your study
- Consent Form Genetic- a consent form designed for a study where genetic testing (as defined by NYS law) is to be done in the CURRENT study
- Consent for studies including genome wide sequencing
- Pediatric Assent Form (To be used in addition to Consent) for Pediatric patients
- Other (e.g., waivers)

Links to the **Standard Consent**, **Genetic Testing Consent** and the **Pediatric Assent** forms can be found in the Help link to the right, or these forms can be downloaded later on in the submission process.

**15.2 \* Indicate the consent process to be used.  
(See Help for CTS SOP)**

Describe how the required information is being presented to subjects (consent form, orally, information sheet, etc.). Attach a copy of what is being presented to subjects (usually the ICF and Assent forms).

Prior to the initiation of any study related procedures, the potential participants will be given a copy of the most recent IRB stamped and approved informed consent to read. Additionally, the PI or study staff member who has been designated to consent will discuss the specifics of the study including but not limited to the purpose of the research, procedures, time commitment, required tasks, test article or device, alternative treatments, benefits, risks, confidentiality etc. in a comprehensible (non-scientific) manner, using language readily understandable by the participant. Participants will be told that participation is voluntary and that, if they do not consent, they will not be penalized. The person consenting will assure the voluntariness of the participant.

Describe the circumstances under which consent will be obtained, where the process will take place and any waiting period between informing the prospective participant and obtaining consent.

A private, confidential setting will be provided for the potential participant to read and discuss the informed consent free from coercion, undue influence or constraints of time. All participants will be given a chance to ask questions and express concerns. They will be given the option to take the consent home and discuss it with family, friends, and /or health care providers. After a participant and the person conducting the consenting signs and dates the consent, the participant will be given a copy of the signed informed consent form. An enrollment note will be written in the source document as to who obtained consent, how, when, were questions asked and answered, and that a copy of the informed consent was given to the participant.

Describe the experience of the investigators designated for this task in the DOA in obtaining consent from subjects.

The following staff, [name], [name] and [name] have extensive experience consenting human participants for participation in research studies.

[name] will undergo consent form training. This competency is based on attending a consenting class which includes regulations, the do's and don'ts and didactic role playing. It also includes observing the consenting process as performed by an experienced consentor and then consenting a participant to participate in a research study while being observed by the experienced consentor.

How will it be determined that the subjects or the subjects' authorized representatives understand the information presented?

The "Teach Back" method will be used in the clinical research setting to ask research participants to repeat or "teach back" the information, concepts and directions that the staff member has attempted to convey to the participant. This method is used to assess comprehension and retention of protocol requirements, adverse event information, risks and benefits, and the participant's rights described in the Informed Consent process.

If English is not the subjects' native language, how will written and/or verbal translation be provided?

For unexpected or isolated participants who are candidates for this study, but for whom English is not a primary language, a translator provided through Pacific Interpreters will be used to facilitate the explanation of the study.

Will any subjects be cognitively impaired so that they may not have the capacity to give consent?

- Yes  No

If yes, Describe the procedures to be used to determine the individual subject's capacity to provide consent.

For subjects where it has been determined that they lack the capacity to give consent, describe the provisions for obtaining consent from the subjects' legally authorized representative.

NA

**15.3 \* Based on the demographics, will this study's subject population require foreign language consent form?**

- Yes  No

If Yes, please list the language(s):

**15.4 \* This study's consent procedure will require the following waivers:  
(See Help for additional information.)**

- Waiver of one or more elements of informed consent, 45CFR46.116(d)
- Waiver of documentation of informed consent, 45CFR46.117(c)
- No waiver is requested

If a waiver is requested, please explain:

**15.5 \* Does this study include videotaping, photography or other electronic recording of human subjects?**

Yes  No

If Yes, please specify:

## 16.0 Recruitment and Advertising

**For assistance consult CRSO to create a robust Recruitment Plan see Help.**

### 16.1 \* What is the plan for recruitment?

**Overview:**

The CRROSS will prescreen up to 100 volunteers in order to enroll 20 with a metabolic syndrome and 20 healthy controls to achieve the goal of 40 evaluable participants at study completion. Healthy controls will be age matched (+/-5 years) and gender matched to the metabolic syndrome participants.

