**11.8 \* Data Analysis**

Describe method(s) of data analysis. Include the role of external collaborators as appropriate.

As per recommended by the food and drug administration (17), the hemagglutination inhibition (HI) antibody assay has been used to assess vaccine activity and may be appropriate for the evaluation of the pandemic influenza vaccine. Appropriate endpoints may include: 1) the percentage of subjects achieving an HI antibody titer  $\geq 1:40$ , and 2) rates of seroconversion, defined as the percentage of subjects with either a pre-vaccination HI titer  $< 1:10$  and a post vaccination HI titer  $> 1:40$  or a pre-vaccination HI titer  $\geq 1:10$  and a minimum four-fold rise in post-vaccination HI antibody titer. Previous study have built models using both HAI and neutralization assays to determine vaccine responsiveness.

The RNA-seq analysis will be run with the help of the Genome resource center as well as the expertise of [name] listed as a collaborator of this project.

**11.9 \* Explain the rationale for the choice of statistical measures and the number of subjects proposed for the study, including the power calculations when applicable.**

Since no preliminary data is available to estimate the percentage of participants achieving a determined level for the HI antibody titer and the rate of seroconversion for each group (healthy volunteers and metabolic syndrome participants) we provide an estimation of the minimum effect size for the sample size selected is able to detect. For a sample size of 40 participants, 20 at each group, a 95% significant Chi-square test will be able to detect an effect size equal or larger than 0.56 with 0.8 power. It means that a Chi-square test will be able to detect independence between groups if the distance between the observed odd ratio is larger than 1.56.

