**12.6 Vulnerable Populations**

Indicate whether any of the following populations will be included in the study:

- Children  
 Pregnant Women  
 Cognitively Impaired Persons  
 RU Employees  
 RU Students  
 Fetal Tissue or Embryonic Stem Cells  
 Induced Pluripotent Stem Cells  
 Other:

If you checked any of the above, give a brief explanation of the need to use these particular individuals:

Special precautions will be used in recruiting employees of the Rockefeller University to minimize the possibility of undue influence. Rockefeller University employees will be made aware of the study through flyers rather than directed presentation to selected groups. Subjects will be reassured that refusal to participate in the study will not affect their studies or employment in any way

If the subject is a Rockefeller University employee, does she/he work within the Laboratory of the Principal Investigator or Co-Investigator(s)?

- Yes  
 No  
 N/A

If the subject is a Rockefeller University student, does she/he work within the Laboratory of the Principal Investigator or Co-Investigator(s)?

- Yes  
 No  
 N/A

**12.7 \*What is the total number of evaluable participants you plan to enroll at Rockefeller University Hospital over the course of the entire study?**

40

**12.8 \* What is the total number of participants who will need to sign consent at Rockefeller University Hospital over the course of the entire study to result in the desired number of evaluable subjects?**

100

**12.9 \* What is the total number of participants you plan to sign consent at Rockefeller University Hospital in the next year?**

100

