**Feasibility and Assessment:**

**Incentives:** 1) Compensation for efforts; 2) Altruism; 3) Free FDA-approved flu vaccine **Challenges:** 1) Many individuals do not self-identify as having metabolic syndrome (may not know diagnosis); 2) Multiple visits within the first week; 3) Lengthy gap between 5th and 6th visit, which may result in attrition, 4) Participants must have untreated metabolic syndrome.

**Issues relevant to rapid accrual:** *Availability of the target population:* A previous study that recruited a similar population (JWA-0786) required prescreening 325 individuals for the investigator to enroll 28 participants across the span of 2 years. The age upper limit of the current study, age 50, limits the eligible population. A NHLBI publication of prevalence by age group of metabolic syndrome of participants in the HUNT2 study suggests that the eligible population will increase (+30% for men, +40% for women) by including the 50-59 year old age group. A feasibility query of the Research Participant Repository reveals 17 potentially eligible volunteers of age 18-50, as well as an additional 22 potentially eligible volunteers aged 51-59. These volunteers are predominantly male due to restrictions of prior studies. *Study burdens:* Another study (TWA-0804) enrolled healthy volunteers to receive FDA-approved vaccines, with a similar duration and shorter between-visit follow-up period; that study enrolled 86 on-study of whom 15 dropped out before the 3 month final visit. *Time Constraints:* Due to vaccination and multiple visits in the first few days, Day 0 visits cannot occur on Fridays. Also, the flu season is limited; interest in the flu vaccine will likely wane by March so the enrollment window is brief.

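### The sample size assumes no loss after enrolment, although the plan cites 17% loss by 3 months in a similar vaccine study; about 33 of the 40 would be evaluable at Day 90

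*Combined protocol and SAP*

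**What the plan says.** The recruitment overview in section 16.1 of the combined protocol and SAP plans to "enroll 20 with a metabolic syndrome and 20 healthy controls to achieve the goal of 40 evaluable participants at study completion". The other counts agree. Item 12.7 asks "What is the total number of evaluable participants you plan to enroll at Rockefeller University Hospital over the course of the entire study" and the answer is 40; item 12.10 also gives 40 and the projected enrolment table in 12.3 totals 40.

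The sample-size rationale in section 11.9 uses the same number: "For a sample size of 40 participants, 20 at each group". It says that a "95% significant Chi-square test will be able to detect an effect size equal or larger than 0.56 with 0.8 power".

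The feasibility text in 16.1 lists the long gap between the fifth and sixth visits as a challenge "which may result in attrition". It then cites an earlier study of healthy volunteers given approved vaccines, similar in duration but with shorter intervals between visits, and reports that "that study enrolled 86 on-study of whom 15 dropped out before the 3 month final visit".

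The figure 100 appears twice. Item 12.8 gives it as the number who must sign consent to yield the evaluable participants. Section 16.1 gives it as the upper limit on volunteers prescreened. Neither place mentions replacing people who leave after enrolment, and no dropout allowance appears elsewhere.

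Section 11.7 draws antibody samples after vaccination at Day 28 and Day 90. The primary outcome in 11.5 names no time point.

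**The concern.** If 40 are enrolled and 40 are to be evaluable at the end, nobody may be lost. The plan's only retention evidence points the other way. The detectable effect in 11.9 is therefore stated for a sample larger than the plan's own figures lead one to expect at Day 90.

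The study would then report on fewer people than its size rationale assumes, with no prior statement of who counts as evaluable or at which visit. With 20 per group, losing three or four from each is a noticeable share of the information.

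**Working it through.** **Inputs.** Enrolment is 20 + 20 and the evaluable target is 40 (16.1, 12.7). The stated power is 0.8 at effect size 0.56 with N = 40 (11.9). Loss in the cited study is 15 of 86 (16.1). A significance level of 0.05 is my reading of the 95% in 11.9. The effect-size metric is not named, and no event rates are given: "no preliminary data is available to estimate the percentage of participants achieving a determined level for the HI antibody titer".

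**1. The plan's own power figure at N = 40.** For a 2 × 2 chi-square test (1 df), power comes from the noncentral chi-square with noncentrality N × w².

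- Read as Cohen's w: 40 × 0.56² = 12.54, so power is 0.943, not 0.80. The w that gives 0.80 at N = 40 is 0.443.
- Read as Cohen's h with 20 per group, two-sided: power is 0.425. The h needed for 0.80 is (1.960 + 0.842) × √(2/20) = 0.886.
- Section 11.9 also restates the effect as "the distance between the observed odd ratio is larger than 1.56". An odds ratio of 1.56 has power of about 0.09 to 0.10 with 20 per group, for assumed control rates of 0.2 to 0.7.

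The stated 0.8 is not reproduced under any of these readings, before any loss.

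**2. Loss implied by the plan.** 1 − 40/40 = 0%.

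**3. Loss in the cited study.** 15/86 = 17.4%, Wilson 95% CI 10.9% to 26.8%.

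**4. Evaluable number at Day 90 at that loss.** 40 × (1 − 0.174) = 33.0, or 16 to 17 per group. At the limits, 40 × (1 − 0.268) = 29.3 and 40 × (1 − 0.109) = 35.6, so about 29 to 36.

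**5. Effect on power, in relative terms.** Take the effect with exactly 0.80 power at N = 40, which is w = 0.443, and change N only.

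| Evaluable N | Power for w = 0.443 | Detectable w at 0.80 power |
|---|---|---|
| 40 | 0.80 | 0.443 |
| 33 | 0.72 | 0.488 |
| 29 | 0.66 | 0.520 |

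At N = 36 the power is 0.76. From 40 to 33 the detectable effect rises by √(40/33) = 1.10.

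**6. The same loss with 0.56 read as Cohen's w.** At N = 33: 33 × 0.56² = 10.35, power 0.896. At N = 29: 29 × 0.56² = 9.09, power 0.85. On this reading power stays above 0.8 across the loss range.

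**The case against.** The strongest objection concerns power. A reader might infer that dropout takes the stated design below 0.8. The documents do not support that. If 0.56 is Cohen's w, power remains 0.896 at 33; if it is h, or the odds ratio of 1.56, power is far below 0.8 with all 40 present. The 0.72 belongs to an effect, w = 0.443, that the plan does not state. This objection stands, and it limits the power result to a relative one.

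Second, the 100 consents in 12.8 run from consent to evaluable, so they could cover later loss as well as screen failure. The timeline of 10 per month over 5 to 6 months would also give 50 to 60 enrolments. Replacement is therefore not ruled out. But neither margin is described as dropout cover, and every enrolment total is 40. Spare capacity cannot be presumed either: the plan's own precedent is 325 prescreened for 28 enrolled, or 8.6%.

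Third, 17.4% is loss by 3 months in one study of healthy volunteers with a different visit pattern. Loss by Day 28 is unknown and probably smaller. This stands: 33 is a Day 90 planning value and probably conservative for Day 28.

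Fourth, a reader might infer from the reference to study completion that only completers are analysed and that Day 28 titres from later leavers are discarded. The plan does not say so: evaluable is nowhere defined as attending Day 90, and the analysis text in 11.8 and 11.9 restricts nothing to completers. Nor do broken matched pairs matter to the tests. One-to-one pairing is not stated, and the group comparisons of titres and response rates are unpaired.

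**Conclusion.** The point holds as one of internal consistency. The plan's enrolment and evaluable numbers imply zero loss, against its own cited 17.4%. At that rate about 33 of 40 (29 to 36) would be evaluable at Day 90, and an effect with 0.80 power at 40 would have about 0.72 (0.66 to 0.76).

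This assumes that the cited study's loss carries over to this trial, that leavers are not replaced, and that the test is a 1-df chi-square at the 0.05 level. The interval reflects sampling error in the cited study only, not differences between the two studies.

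It does not establish that dropout causes a shortfall from the stated 0.8. That figure needs recalculating whatever the retention.

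**What to change.** - **Sections 12.7 and 16.1:** state the expected evaluable number at Day 90 as about 33 (29 to 36) of 40 enrolled. Define evaluable for the antibody outcome as vaccinated with a pre-vaccination and a Day 28 HI titre. Analyse everyone who meets this, and analyse Day 90 in those who attend.
- **Section 11.9:** recompute the detectable effect from scratch with a named metric, for example Cohen's w at 0.80 power: 0.443 at 40, 0.488 at 33 and 0.520 at 29. Do not scale 0.56 by 1.10, which would carry an unreproduced figure forward. Note that 33 rests on 3-month loss and is probably conservative for Day 28.
- **Sections 12.8 and 16.1:** reconcile 100 consented with 100 prescreened, and say whether that number is meant to cover replacement of people who leave.

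The cost is protocol wording, one recalculation and a less favourable evaluable number. No participants are added. If 20 evaluable per group at Day 90 is held to be essential, that is a separate decision: at the cited rate it needs 20/(1 − 0.174) = 24.2, so 25 enrolled per group.

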**drawn prior to flu vaccine)**

POCT - urine pregnancy test

Adverse event assessment

Administration of the influenza vaccine intramuscularly (IM): Vaccination with quadrivalent 2016-2017 vaccine A/California/7/2009 (H1N1); A/Hong Kong/4801/2014 (H3N2); B/Brisbane/60/2008(B/Victoria lineage); B/Phuket/3073/2013 (B/Yamagata lineage). Participants of normal weight will be injected IM with a needle of 1 to 1.5 in length. Obese individuals (defined as BMI>25) generally will require the use of a 2 in length needle to assure that the injection reaches the muscle. The needle length used for injection will be documented in the medical record.

Total blood volume to be drawn for visit #1 = 26.5ml

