**Order Number    Criteria**

1                      Currently undergoing treatment for the metabolic syndrome

2                      Blood Pressure > 150/90

- 3 NSAIDs and/or Aspirin ingestion within the last 14 days
- 4 Hepatitis A, B and C
- 4 Self-reported history of any active autoimmune diseases
- 5 Self-reported ingestion of statins within the last 3 months
- 6 Self-reported antibiotic use within the last 3 months
- 7 Anti-inflammatories including biologics and corticosteroids within last 3 months( nasal spray and topical applications are OK)or Omega 3 Fatty Acids.
- 8 Self-reported hx of cancer treatment within the last year
- 9 Allergy to eggs
- 10 History of Guillain-Barre syndrome
- 11 Pregnant ( determined by POCT at Screening visit #1 and Study visit #1).
- 12 HIV positive
- 13 Self-reported history of receiving the flu vaccination after June 1, 2016.
- 14 Any self-reported infection in the week of the visit except the first two visits (Screening visit 1 and Screening visit 2) and the last visit (Study visit #5) that could be rescheduled.
- 15 Any medical, psychological or social condition that, in the opinion of the Investigator, would jeopardize the health or well-being of the participant during any study procedures or the integrity of the data.

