**Projected enrollment timeline:** Recruitment initiation will begin as soon the study receives IRB approval, likely in the first or second week of November. The investigator's target of completing accrual by April 2016, which would allow for 5-6 months achieving complete study enrollment. This would require the enrollment of 10 participants (5 metabolic syndrome and 5 age matched controls) per month. The study requires 2 screening visits (1 week start-up lag). The enrollment timeline is ambitious, even assuming a steady flow of participants and likely only feasible using the Repository population and potentially expanding the age range. Based on previous recruitment experience of this population, CRROSS would predict 12- 15 months for study accrual, however given ResearchMatch and Repository resources, 6 months is ambitiously feasible.

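### Vaccine product, and season if more than one contributes, could be confounded with cohort: controls are matched on age and gender only and no analysis adjusts for either

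*Combined protocol and SAP*

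**What the plan says.** **Matching.** Section 16.1 (Overview) gives the whole rule: "Healthy controls will be age matched (+/-5 years) and gender matched to the metabolic syndrome participants". The enrollment timeline in 16.1 mentions age matching only. Neither product nor calendar time is a matching factor.

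**Product.** Section 14.1 lists Fluarix Quadrivalent and, from a second manufacturer, "Fluzone Quadrivalent". Study Visit #1 in 11.7 gives the season and the four strains ("Vaccination with quadrivalent 2016-2017 vaccine") but names no product.

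**Analysis.** Under Statistical Analysis in 11.9, titres are compared by a t-test or Wilcoxon-Mann-Whitney test and responder percentages by a chi-square or Fisher test. The expression model has cohort as its only fixed factor. None of these includes product or season.

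**Season.** The vaccine and the haemagglutination inhibition panel in 11.7 are those of 2016-2017, and exclusion 13 in 12.12 is tied to the same season: "Self-reported history of receiving the flu vaccination after June 1, 2016". Other sections carry earlier dates. IRB approval is 25 November 2015 (9.7) and the accrual target in 16.1 is April 2016. Screening Visit #1-A allows people who failed screening under earlier criteria to be screened again.

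**Accrual.** Section 16.1 reports that "CRROSS would predict 12- 15 months for study accrual", then adds in the same sentence that six months is achievable, if ambitious, with the registry and repository resources. It cites a study of a similar population that "required prescreening 325 individuals for the investigator to enroll 28 participants across the span of 2 years".

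**The concern.** The cohorts are defined by metabolic status and are not randomised, so only matching or adjustment can balance other influences on the antibody response. The plan balances age and gender. If the two products, or two seasons' vaccines, give different titres and are unevenly spread over the cohorts, the unadjusted tests attribute that difference to metabolic syndrome. The error can go either way: it can create a difference or hide a real one.

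The product exposure exists even if all 40 people are vaccinated in one season. The season exposure depends on events the documents leave open. They do not say whether anyone was vaccinated in 2015-2016, whether such people would count toward the 40, or what happens if 2016-2017 does not yield 40.

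**Working it through.** **1. The plan's accrual figures.** The target is 40, 20 per cohort (11.9: "For a sample size of 40 participants, 20 at each group, a 95% significant Chi-square test").

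- Required rate: 16.1 asks for 10 per month, 5 in each cohort. 40/10 = 4 months. The stated 5-6 months needs only 40/6 = 6.7 to 40/5 = 8 per month, so the rate does not reproduce from the target alone.
- Recruitment office forecast: 40/15 = 2.7 to 40/12 = 3.3 per month. The plan expects interest to fade by March. Assuming a 5-month window gives 13 to 17 participants in a season; a 6-month window gives 16 to 20.
- Precedent: 28/24 = 1.17 per month. 20/1.17 = 17.1 months for the metabolic syndrome cohort, and 40/1.17 = 34.3 months for everyone. The 12-15 months does not follow from this rate.

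On the slower figures one season would not suffice; on the six-month figure it could.

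**2. Is the slower forecast current?** The feasibility text in 16.1 assumes an upper age limit of 50; section 12.1 now sets 65. The repository query found 17 potentially eligible people aged 18-50 and 22 more aged 51-59. That is 39 in all, or 39/17 = 2.3 times the pool, before counting ages 60-65. The forecast therefore predates a change that eases recruitment.

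**3. Size of the bias.** For a factor with two levels (product or season):

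spurious log2 difference = (share in one cohort − share in the other) × effect in log2 units.

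The documents give no effect, so 1.5-fold and two-fold are assumptions.

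| Split, of 20 v 20 | Difference in share | Spurious ratio, 1.5-fold effect | Spurious ratio, two-fold effect |
|---|---|---|---|
| 10 v 10 | 0 | 1.00 | 1.00 |
| 12 v 8 (60% v 40%) | 0.2 | 1.08 | 2^0.2 = 1.15 |
| 14 v 6 (70% v 30%) | 0.4 | 1.5^0.4 = 1.18 | 2^0.4 = 1.32 |
| 15 v 5 | 0.5 | 1.22 | 1.41 |
| 18 v 2 | 0.8 | 1.38 | 1.74 |

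**4. False-positive rate for the responder comparison.** This is an exact enumeration of the planned rule (chi-square, or Fisher if any observed cell is below 5) with 20 v 20, no true cohort effect and responses centred on 50%. The product or season effect is assumed, in percentage points.

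| Split | 10 points | 20 points | 30 points | 40 points |
|---|---|---|---|---|
| 10 v 10 | 3.8% | 3.5% | 3.0% | 2.4% |
| 12 v 8 | 3.9% | 4.1% | 4.3% | 4.6% |
| 15 v 5 | 4.7% | 7.5% | 12.3% | 19.5% |
| 18 v 2 | 6.3% | 14.4% | 29.0% | 49.4% |

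A 12 v 8 split stays below 5% throughout. Clear inflation needs a marked imbalance together with a sizeable effect.

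**The case against.** The strongest case against the point is that the text fixes one season. Vaccine, panel and exclusion 13 all refer to 2016-2017, so vaccination in any other season would need an amendment. Section 12.9 plans all 100 consents, the whole-study total in 12.8, within the next year. Section 13.1 projects 240 outpatient visits in that year, which equals 40 × 6. The 5 + 5 monthly projection implies that the cohorts accrue side by side. Listing two products does not show that both will be used; they share a strain set and a 0.5 mL presentation. Seroconversion is also measured against each person's own baseline, which offsets part of any difference in starting titres.

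Most of this stands, and it rules out some stronger readings that a reader might infer:

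- *That accrual will run over several seasons.* The 12-15 month forecast is followed by the six-month alternative and rests on the old age limit. The three-year duration in 9.8 is for the study, not for accrual.
- *That controls will systematically be vaccinated later than their matches.* Nothing says so, and the projection is for concurrent accrual.
- *That exclusion 13 changes meaning in 2017-2018, or that later participants would meet the wrong strain panel.* The current text authorises no such vaccination.

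The objection does not remove the product gap. The 5 + 5 figure is a projected rate, not an enrolment rule, and it says nothing about product. Nor does the one-season wording settle the status of anyone vaccinated under the earlier criteria.

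**Conclusion.** The point holds in limited form. Nothing in the matching rule, the vaccine section or the analysis keeps product balanced between cohorts, and product could be confounded with cohort whatever the length of accrual. Season could be confounded only if 2015-2016 participants count toward the 40, or if an overrun leads to an amendment for a later season.

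The documents supply no product or season effect. Under an assumed two-fold effect, the spurious titre ratio is 1.15 at 60% v 40% and 1.32 at 70% v 30%. The false-positive rate for the responder test is close to nominal or below it under mild imbalance, and rises materially only in the more extreme assumed cases. This is a worthwhile and inexpensive safeguard, not evidence that the comparison is already biased.

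**What to change.** In 16.1, either use a single product for all participants, or require each control to receive the same product in the same flu season as the matched participant. Both bring the difference in share, and so the bias in step 3, to zero. Record product, lot and season for everyone.

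In 11.9, state that if more than one product or season contributes, the comparisons will be stratified or adjusted for it: a stratified test for titres and responder rates, and a fixed effect in the expression model. In that case each participant's serum should be assayed against the strains of the vaccine received. Adjustment cannot help if one cohort receives only one product and the other cohort only the other, so the design rule comes first.

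State whether any 2015-2016 participants count toward the 40. Reconcile the April 2016 accrual target and the age-50 feasibility text with the 2016-2017 vaccine and the age limit of 65.

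The cost is a wording amendment and slightly less flexibility in vaccine supply and in pairing controls. The sample size stays at 40. No fixed interval between the vaccination of a participant and of the matched control is needed; with so small a recruitment pool it could slow accrual.
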